### **EXTENT OF EXPOSURE**

The number of subjects in each study arm, the number of days/cycles on treatment, quantity of study drug administered, and the number of subjects requiring dose reductions, treatment interruption, and treatment discontinuation will be summarized by study arm.

### **ADVERSE EVENTS**

AEs will be graded using CTCAE v5.0. Investigators will collect all AE CTCAE grades (for both increasing and decreasing severity). AEs will be classified into standardized medical terminology from the verbatim description (investigator term) using the Medical Dictionary for Regulatory Activities (MedDRA). AEs will be presented by preferred term (PT) nested within system organ class (SOC). Verbatim descriptions and MedDRA SOC PT for all AEs will be contained in the data listings of the clinical study report for this protocol.

An overview table, including the incidence of and the number of subjects with treatment-emergent adverse events (TEAEs), SAEs, deaths, and those TEAEs that led to discontinuation, dose modification, or dose interruption, will be provided.

The incidence of TEAEs will be summarized by SOC, PT, CTCAE grade, and relatedness to study drug. Although a MedDRA term may be reported more than once for a subject, that subject will be counted only one time in the incidence count for that MedDRA term with the highest CTCAE grade (in the summary by CTCAE grade) or with the closest relationship to study treatment (in the summary by relatedness to study treatment).

TEAEs will be analyzed. AEs that are not treatment-emergent will be listed. TEAEs are defined as AEs that emerge during treatment, having been absent at pretreatment (baseline), or those that:

- Reemerge during treatment, having been present at baseline but stopped prior to treatment, or
- Worsen in severity during treatment relative to the pretreatment state, when the AE is continuous.

Separate summary tables will be provided for all TEAEs, treatment-emergent SAEs, TEAEs

reported as treatment-related, treatment-emergent SAEs reported as treatment-related, and TEAEs leading to treatment discontinuation.

### **LABORATORY VALUES**

Clinical laboratory values will be evaluated for each laboratory parameter by subject. Abnormal laboratory values will be identified as those outside (above or below) the normal range. Reference (normal) ranges for laboratory parameters will be included in the clinical study report for this protocol. Descriptive summary statistics for laboratory parameters and their changes from baseline will be calculated.

Laboratory parameters that are graded in CTCAE v5.0 will be summarized by CTCAE grade.

Clinical laboratory results postbaseline will be evaluated for markedly abnormal values. The National Cancer Institute's CTCAE v5.0 will be used to identify subjects with markedly abnormal laboratory values. The incidence of markedly abnormal values will be summarized by cycle. For the incidence of markedly abnormal laboratory values, each subject may be counted once in the laboratory parameter value high category and once in the laboratory parameter low category, as applicable.

### **VITAL SIGNS**

Descriptive statistics for vital signs parameters (i.e., sitting diastolic and systolic BP, sitting pulse rate, respiratory rate, temperature, weight, and changes from baseline) will be presented by visit.

### **ECGs**

Analysis of any drug effect on QT/QTcF will be described in the SAP.

## **9.7.2 Determination of Sample Size**

### **LEAD-IN PART**

The number of subjects in the Lead-In part will be approximately 20, based on the CRM design requirements.

### **MAIN STUDY**

The sample size of approximately 70 Stage I – III subjects (including Stage I – III subjects from both the Main Study plus from the Lead-In part 9 µg/kg/day dose group combined) was estimated assuming that a lower limit of the 2-sided 95% CI of ORR exceeding 25% indicates clinical benefit in persistent and recurrent CTCL. It was also assumed that in this population we can reasonably expect to observe an ORR  $\geq$  36%, i.e., at least 25 subjects with CR+PR among 70 subjects.

With a sample size of approximately 70 Stage I – III subjects (including Stage I – III subjects from both the Main Study plus from the Lead-In part 9 µg/kg/day dose group combined), the 2-sided 95% exact Clopper–Pearson CI of an observed 36% ORR would range from 25% to

48%. Thus, an observed ORR that is  $\geq 36\%$  would be significantly higher than 25%, thereby demonstrating the presence of clinical benefit.

Sample size estimates were calculated using PASS 2008 software.

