#### **Sample size for Main Study**

The sample size of approximately 70 Stage I – III subjects (including Stage I – III subjects from both the Main Study plus from the Lead-In part 9 µg/kg/day dose group combined) was estimated assuming that the lower limit of the 2-sided 95% CI of ORR exceeding 25% indicates clinical benefit in persistent and recurrent CTCL; and that in this population we can reasonably expect to observe an ORR  $\geq$  36%, i.e., at least 25 subjects with CR+PR among 70 subjects.

With a sample size of approximately 70 Stage I – III subjects (including Stage I – III subjects from both the Main Study and from the Lead-In part 9 µg/kg/day dose group), the 2-sided 95% exact Clopper-Pearson confidence interval of an observed 36% ORR would range from 25% to 48%. Thus, an observed ORR that is  $\geq$  36% would be significantly higher than 25%, thereby demonstrating the presence of clinical benefit.

Sample size estimates were calculated using PASS 2008.

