#### **PRIMARY EFFICACY ANALYSIS**

The primary endpoint ORR will be analyzed on the full analysis set. ORR will be calculated in Stage I – III CTCL subjects from the Main Study plus the Lead-In subjects from the 9µg/kg/day dose group combined, using a 2-sided, exact 95% confidence interval (CI), using the Clopper-Pearson method. The treatment will be considered efficacious and demonstrating clinical benefit of E7777 if the lower limit of the 2-sided 95% exact CI of the observed ORR exceeds 25%.

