5 DETERMINATION OF SAMPLE SIZE

The sample size of approximately 70 Stage I - III subjects (including Stage I - III subjects from both the Main Study and the Lead-In part 9µg/kg/day dose group combined) was estimated assuming that the lower bound of the 2-sided 95% Confidence Interval (CI) of ORR exceeding 25% which indicates clinical benefit in persistent and recurrent CTCL. With a sample size of 70, the 2-sided 95% exact Clopper-Pearson confidence interval of an

observed 36% ORR (i.e., 25 subjects with CR+PR among 70 subjects) would be with lower bound of 25% and upper bound of 48%.

Sample size estimates were calculated using PASS 2008 software.

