6.5.1 Primary Efficacy Analysis

The primary endpoint is the ORR based on Olsen (2011)¹ criteria, using response assessment data by IRC. The ORR is the proportion of subjects achieving a BOR of confirmed CR or PR. The Primary Efficacy Analysis Set will be used for analysis.

The 2-sided, exact 95% CI of ORR will be calculated using the Clopper-Pearson method. The treatment will be considered efficacious and demonstrating the clinical benefit of E7777 if the lower bound of the 2-sided 95% exact CI of the observed ORR exceeds 25%.

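### 25 responders out of 70 fail the 25% success rule (exact lower limit 24.6%), yet the sample-size sections rest on that count and the protocol calls it significant

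*Protocol*

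**What the plan says.** **Decision rule.** Protocol 9.7.1.7 (Primary Efficacy Analysis) calculates the ORR "using a 2-sided, exact 95% confidence interval (CI), using the Clopper-Pearson method". It declares efficacy "if the lower limit of the 2-sided 95% exact CI of the observed ORR exceeds 25" percent. The Synopsis has the same rule, and SAP 6.5.1 repeats it: "if the lower bound of the 2-sided 95% exact CI of the observed ORR exceeds 25" percent. The inequality is strict, and none of these places mentions rounding or a responder count.

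**Sample size, protocol.** The Synopsis and 9.7.2 plan for about 70 Stage I–III subjects. They expect to observe an ORR of 36% or more, spelled out as "at least 25 subjects with CR+PR among 70 subjects". They give the exact interval at 36% as 25% to 48% and conclude that an observed ORR of 36% or more "would be significantly higher than 25%, thereby demonstrating the presence of clinical benefit".

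**Sample size, SAP.** Section 5 supports 70 subjects with the same example, an "observed 36% ORR (i.e., 25 subjects with CR+PR among 70 subjects) would be with lower bound of 25% and upper bound of 48" percent. It does not add the sentence about significance.

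Neither document states a power or a probability of success.

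**The concern.** The printed lower limit equals the threshold, and the rule requires it to be above the threshold. Even at face value, a limit of 25% does not exceed 25%. The response rate (35.7% shown as 36%) and the lower limit are both given as whole percents, so rounding could decide whether the example passes.

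This is a single-arm registrational study with one primary test. If exactly 25 of 70 subjects respond, the sample-size section of the protocol calls the result significant and the decision rule calls it a failure. That dispute would fall on the boundary result, where pre-specification matters most. The case for 70 subjects also rests on this example, so if 36% lies below the real cut-off, the example does not support the sample size.

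**Working it through.** **Inputs**
- Threshold 25%, limit must exceed it: Protocol 9.7.1.7, SAP 6.5.1.
- Method: two-sided 95% Clopper-Pearson, 0.025 in each tail: same sections.
- n = 70 and x = 25: Protocol 9.7.2, SAP 5.
- 38%, the ORR quoted for the reference product in 263 subjects: Protocol 7.3.1.

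**Formulas**
- Lower limit = 0.025 quantile of Beta(x, n − x + 1).
- Upper limit = 0.975 quantile of Beta(x + 1, n − x).
- Equivalent test: the lower limit exceeds 25% exactly when P(X ≥ x | n, 0.25) < 0.025.
- Probability of success at true rate p = P(X ≥ c | n, p), where c is the smallest passing count.

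**Step 1. Reproduce the plan's interval.** For 25/70 = 35.7%, Beta(25, 46) and Beta(26, 45) give 24.61% and 48.07%. To whole percents this is the printed 25% to 48%, so the interval reproduces.

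**Step 2. Apply the rule without rounding.** 24.61% is below 25%, and P(X ≥ 25 | 70, 0.25) = 0.0299 is above 0.025. Both forms say that 25/70 fails.

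**Step 3. Find the smallest passing count.** For 26/70 = 37.1%, the interval is 25.89% to 49.52% and P(X ≥ 26 | 70, 0.25) = 0.0163. It passes, so c = 26.

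**Step 4. Could another reading rescue 25/70?**

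| Reading | Lower limit | Above 25%? |
|---|---|---|
| Exactly 36% (25.2/70), same formula | 24.87% | no |
| Wald, 25/70 | 24.5% | no |
| Jeffreys, 25/70 | 25.2% | yes |
| Wilson, 25/70 | 25.5% | yes |
| One-sided 95% exact, 25/70 | 26.2% | yes |

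The readings that pass are not the specified method.

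**Step 5. Probability of success at n = 70.**

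| True ORR | 26 or more (the rule) | 25 or more (the protocol's example) |
|---|---|---|
| 25% (type I error) | 1.6% | 3.0% |
| 36% | 46.6% | 56.5% |
| 38% | 60.3% | 69.5% |
| 40% | 72.7% | 80.3% |

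Under the rule, the probability reaches 80% at a true ORR of about 41.4% and 90% at about 44.0%.

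**Step 6. Let n vary, since the plan says approximately 70.**

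| Final n | Minimum responders |
|---|---|
| 65 | 24 |
| 66–68 | 25 |
| 69–72 | 26 |
| 73–75 | 27 |

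Twenty-five responders pass at n = 68 (25.39%) and just fail at n = 69 (24.995%). The 69-subject case shows why the comparison must be made unrounded.

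**The case against.** **The rule is right, and the count is only an illustration.** The efficacy sections ask for the exact limit and name no count. If they are followed, the type I error at 70 subjects is 1.6%; the 3.0% arises only if someone applies the example instead. This stands, and the rule needs no change. It does not make the protocol's conclusion about 25/70 true.

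**The SAP does not make the false statement.** Section 5 gives a correctly rounded interval and never says that 25/70 succeeds. This also stands: the explicit error is in the protocol. The SAP's fault is that it justifies the sample size with a count that fails its own rule, at a precision that hides the failure.

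**Taken literally, 36% or more of 70 means 26 subjects.** 0.36 × 70 = 25.2, so a whole count must be 26, and 26 passes. But both documents fix the count themselves at 25, so this reading does not rescue the text.

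**n is only approximate.** At n = 75, exactly 36% (27/75) passes with a limit of 25.23%. That is a reason to tabulate the minimum count by n. It does not repair the example, which is stated for 70.

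**36% is a floor for the observed rate, not an assumed true rate.** This is fair. The 46.6% therefore describes the bottom of the expected range, and the probabilities at 38% and 40% should be read beside it.

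**Conclusion.** The concern holds. Under the plan's own method and threshold, 25/70 fails (lower limit 24.61%) and 26/70 is the smallest success (25.89%). The protocol's statement in the Synopsis and 9.7.2 that the 25-of-70 result is significantly above 25% is wrong. SAP 5 carries the same count as its sample-size justification without drawing that conclusion.

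The error is one responder, but it falls on the primary success threshold. Acting on the example would mean a one-sided type I error of 3.0% instead of 1.6%. At a true ORR of 36%, the bottom of the range the plan expects, the trial is slightly more likely to fail than to succeed (46.6%). At the reference product's 38% the chance of success is 60.3%.

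These figures assume exactly 70 subjects in the primary efficacy set, independent binomial responses with a common rate, and an unrounded comparison with 25%. The correction should be made before the analysis, although the decision rule itself is sound.

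**What to change.** 1. In the Synopsis, Protocol 9.7.2 and SAP 5, replace the 25-of-70 example with 26 of 70 (37.1%), exact 95% interval 25.9% to 49.5%. In the protocol, restate the significance sentence for that count.
2. In Protocol 9.7.1.7, its Synopsis counterpart and SAP 6.5.1, add that the lower limit is compared with 25% before any rounding. Leave the rule otherwise as it is.
3. Add the table of minimum responders by final n: 65: 24; 66–68: 25; 69–72: 26; 73–75: 27.
4. State the probability of success for 70 subjects at a range of true rates: 46.6% at 36%, 60.3% at 38%, 72.7% at 40%, 80% at about 41.4% and 90% at about 44.0%.

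The cost is wording in the two documents. No patients are added and no analysis changes. The stated operating characteristics become somewhat less favourable.

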### 9.7.3 Interim Analysis

At the end of the Lead-In part of the study, the objective response of all subjects will be evaluated. The study will only continue to the Main Study if there is at least one subject in the Lead-In with a confirmed CR or PR by investigator assessment.

### 9.7.4 Procedure for Revising the SAP

If the SAP needs to be revised after the study starts, the sponsor will determine how the revision impacts the study and how the revision should be implemented. The details of the revision will be documented and described in the clinical study report.

## **11 PROCEDURES AND INSTRUCTIONS (ADMINISTRATIVE PROCEDURES)**

### **11.1 Changes to the Protocol**

Any change to the protocol requires a written protocol amendment or administrative change that must be approved by the sponsor before implementation. Amendments specifically affecting the safety of subjects, the scope of the investigation, or the scientific quality of the study require submission to health or regulatory authorities as well as additional approval by the applicable IRBs/IECs. These requirements should in no way prevent any immediate action from being taken by the investigator, or by the sponsor, in the interest of preserving the safety of all subjects included in the study. If the investigator determines that an immediate change to or deviation from the protocol is necessary for safety reasons to eliminate an immediate hazard to the subjects, the sponsor's medical monitor and the IRB/IEC for the site must be notified immediately. The sponsor must notify the health or regulatory authority as required per local regulations.

Protocol amendments that affect only administrative aspects of the study may not require submission to health or regulatory authority or the IRB/IEC, but the health or regulatory authority and IRB/IEC (or, if regionally required, the head of the medical institution) should be kept informed of such changes as required by local regulations. In these cases, the sponsor may be required to send a letter to the IRB/IEC and the CA (or, if regionally required, the head of the medical institution) detailing such changes.

### **11.2 Adherence to the Protocol**

The investigator will conduct the study in strict accordance with the protocol (refer to ICH E6, Section 4.5).

### **11.3 Monitoring Procedures**

The sponsor's CRA will maintain contact with the investigator and designated staff by telephone, letter, or email between study visits. Monitoring visits to each site will be conducted by the assigned CRA as described in the monitoring plan. The investigator (or, if regionally required, the head of the medical institution) will allow the CRA to inspect the clinical, laboratory, and pharmacy facilities to assure compliance with GCP and local regulatory requirements. The CRFs and subject's corresponding original medical records (source documents) are to be fully available for review by the sponsor's representatives at regular intervals. These reviews verify adherence to study protocol and data accuracy in accordance with local regulations. All records at the site are subject to inspection by the local auditing agency and IRB/IEC review.

In accordance with ICH E6, Section 1.52, source documents include, but are not limited to the following:

- Clinic, office, or hospital charts

- Copies or transcribed health care provider notes which have been certified for accuracy after production
- Recorded data from automated instruments such as IxRS, x-rays, and other imaging reports (e.g., sonograms, CT scans, magnetic resonance images, radioactive images, ECGs, rhythm strips, electroencephalograms, polysomnographs, pulmonary function tests), regardless of how these images are stored, including microfiche and photographic negatives
- Pain, QoL, or medical history questionnaires completed by subjects
- Records of telephone contacts
- Diaries or evaluation checklists
- Drug distribution and accountability logs maintained in pharmacies or by research personnel
- Laboratory results and other laboratory test outputs (e.g., urine pregnancy test result documentation and urine dip-sticks)
- Correspondence regarding a study subject's treatment between physicians or memoranda sent to the IRBs/IECs
- CRF components (e.g., questionnaires) that are completed directly by subjects and serve as their own source

#### **11.4 Recording of Data**

A CRF is required and must be completed for each subject by qualified and authorized personnel. All data on the CRF must reflect the corresponding source document, except when a section of the CRF itself is used as the source document. Any correction to entries made on the CRF must be documented in a valid audit trail where the correction is dated, the individual making the correction is identified, the reason for the change is stated, and the original data are not obscured. Only data required by the protocol for the purposes of the study should be collected.

The investigator must sign each CRF. The investigator will report the CRFs to the sponsor and retain a copy of the CRFs.

#### **11.5 Identification of Source Data**

All data to be recorded on the CRF must reflect the corresponding source documents. For the following items, the data recorded directly on the CRF are to be considered source data:

- Study drug compliance (e.g., the reason for the change of dosing)
- Information on the subject's discontinuation (e.g., in the case of lost to follow-up due to the subject choice)

- PK sampling date and time
- Clinical laboratory test sampling date
- Comments and relevant information on the AEs (e.g., severity, relationship to study drug, outcome)

## **11.6 Retention of Records**

The circumstances of completion or termination of the study notwithstanding, the investigator (or, if regionally required, the head of the medical institution or the designated representative) is responsible for retaining all study documents, including but not limited to the protocol, copies of CRFs, the IB, and regulatory agency registration documents (e.g., Form FDA 1572, ICFs, and IRB/IEC correspondence). In addition, the sponsor will send a list of treatment codes by study subject to the investigator after the clinical database for this study has been locked. The site should plan to retain study documents, as directed by the sponsor, for at least 2 years after the last approval of a marketing application in an ICH region and until there are no pending or contemplated marketing applications in an ICH region or at least 3 years have elapsed since the formal discontinuation of clinical development of the investigational product.

It is requested that at the completion of the required retention period, or should the investigator retire or relocate, the investigator contact the sponsor, allowing the sponsor the option of permanently retaining the study records.

## **11.7 Auditing Procedures and Inspection**

In addition to the routine monitoring procedures, the sponsor's Clinical Quality Assurance department conducts audits of clinical research activities in accordance with the sponsor's Standard Operating Procedures (SOPs) to evaluate compliance with the principles of ICH, GCP, and all applicable local regulations. If a government regulatory authority requests an inspection during the study or after its completion, the investigator must inform the sponsor immediately.

## **11.8 Handling of Study Drug**

All study drugs will be supplied to the investigator (or a designated pharmacist) by the sponsor. Drug supplies must be kept in an appropriate secure area (e.g., locked cabinet) and stored according to the conditions specified on the drug labels. The investigator (or a designated pharmacist) must maintain an accurate record of the shipment and dispensing of the study drug in a drug accountability ledger, a copy of which must be given to the sponsor at the end of the study. An accurate record of the date and amount of study drug dispensed to each subject must be available for inspection at any time. The CRA will visit the site and review these documents along with all other study conduct documents at appropriate intervals once study drug has been received by the site.

All drug supplies are to be used only for this study and not for any other purpose. The investigator (or site personnel) must not destroy any drug labels or any partly used or unused drug supply prior to approval to do so by the sponsor. At the conclusion of the study and as

appropriate during the study, the investigator (or a designated pharmacist) will return all used and unused drug containers, drug labels, and a copy of the completed drug disposition form to the sponsor's CRA or, when approval is given by the sponsor, will destroy supplies and containers at the site.

## **11.9 Publication of Results**

All manuscripts, abstracts, or other modes of presentation arising from the results of the study must be reviewed and approved in writing by the sponsor in advance of submission pursuant to the terms and conditions set forth in the executed Clinical Trial Agreement between the sponsor and the institution/investigator. The review is aimed at protecting the sponsor's proprietary information existing either on the date of the commencement of the study or generated during the study.

The detailed obligations regarding the publication of any data, material results, or other information, generated or created in relation to the study shall be set out in the agreement between each investigator and the sponsor.

